**Table 1. PK Sampling Table**

Study Period	Treatment Period 1		Treatment Period 2	Treatment Period 3	Treatment Period 4									
	Day 1 Abd Inj	Wk 10 Abd Inj	Wk 16 Abd Inj	Wk 22 Abd Inj	Wk 24 Abd Inj	Wk 26 Abd Inj	Wk 28 Abd Inj	Wk 30 Abd Inj	PK Day 3	PK Day 4	PK Day 5	PK Day 7	PK Day 11	Wk 32
PK Profile Day								1	3	4	5	7	11	15
Time (h) Post-Dose	0 a,b	0 a,b	0 a,b	0 a,b	0 a,b	0 a,b	0 a,b	0 a,b	48	72	96	144	240	336 a
PK Tolerance Window (h) d	-48	-48	-48	-6	-6	-6	-6	-6 c	±4 c	±6 c	±8 c	±8 c	±24 c	±24 c

- Predose PK sample.
- Injection on-site.
- PK sample must fall within the PK sampling time window for the participant to be Per Protocol (for the primary endpoint).
- Blood samples for determination of adalimumab trough drug concentrations will be collected within 6 hours prior to the investigational product administration on Weeks 22, 24, 26, 28, and on Day 1 (time 0), Weeks 10 and 16 at a maximum of 48 hours prior to, but as close as possible prior to the next investigational product administration (ie, pre-dose). The 2-week PK sampling period starts with Week 30 predose PK collection and end with Week 32 predose PK collection. Blood samples for determination of adalimumab drug concentrations for the 2-week PK profile will be collected starting with the Week 30 injection of investigational product (PK Profile Day 1): blood will be collected within 6 hours prior to investigational product administration. For the subsequent PK Profile Days, post-Week 30 dosing times for serum collections are 48 (±4) hrs on PK Profile Day 3, 72 (±6) hrs on PK Profile Day 4, 96 (±8) hrs on PK Profile Day 5, 144 (±8) hrs on PK Profile Day 7, 240 (±24) hrs on PK Profile Day 11, and 336 (±24) hrs on PK Profile Day 15. **Every effort should be made to draw samples within the specified time windows.** The 2-week PK Profile collections may be completed using home health care service

Abbreviations: Abd = abdominal; h = hour; Inj = injection; PK = pharmacokinetic; Wk = week.

## 2. INTRODUCTION

Adalimumab (marketed under the brand name HUMIRA®) is a recombinant fully human Immunoglobulin G1 (IgG1) monoclonal antibody (mAb) that specifically binds to TNF $\alpha$  and blocks its interaction with the p55 and p75 cell surface TNF receptors, thereby neutralizing the effect of TNF in inflammatory conditions. HUMIRA is approved for use in both the United States (US) and European Union (EU) for the treatment of rheumatoid arthritis (RA), ankylosing spondylitis (AS), psoriatic arthritis (PSA), polyarticular juvenile idiopathic arthritis, Crohn's disease (CD), pediatric CD, ulcerative colitis (UC), plaque psoriasis (PS), adult and adolescent hidradenitis suppurativa (HS), and pediatric and adult uveitis (UV); it is also approved in the EU for axial spondyloarthritis (radiographic-negative), pediatric plaque psoriasis, and juvenile enthesitis-related arthritis.

PF-06410293 is a fully human IgG1 monoclonal antibody (mAb) and has been approved by the FDA as a biosimilar of adalimumab, also referred by the brand name HUMIRA in this protocol. The general term “adalimumab” is sometimes used for convenience when discussing the treatments in the 2 arms: switching and non-switching.

## 2.1. Study Rationale

The purpose of the trial is to support obtaining the FDA's interchangeability designation, not to re-establish "PK equivalence" between licensed Humira and PF-06410293. The objectives and design of this study are generally consistent with recommendations found in the corresponding FDA Interchangeability guidance. In reference to a biological product, interchangeability means that "the biological product may be substituted for the reference product without the intervention of the health care provider who prescribed the reference product". This study has been designed with input from FDA to deliver sufficient information to support the interchangeability of PF-06410293 with the reference product, Humira.

## 2.2. Background

Pfizer is developing PF-06410293 as a biosimilar and interchangeable product to Humira. Biosimilarity has been established through quality, nonclinical, and clinical assessments. Regulatory approval for PF-06410293 as a biosimilar to Humira was received from United States (US) Food and Drug Administration (FDA). Pfizer seeks to demonstrate that PF-06410293 is interchangeable under Section 351(k)(4) of the PHS Act (FDA Guidance 2015). A designation of interchangeability means that 'the risk in terms of safety or diminished efficacy of alternating or switching between use of the biological product and the reference product is not greater than the risk of using the reference product without such alternation or switch' (FDA Guidance, 2019).

This IC study has been designed to support the FDA interchangeability designation.

Humira is approved for use in both the United States (US) (first licensed on 31 December 2002) and European Union (EU) (first authorized on 8 September 2003).

### 2.2.1. Clinical Overview

The clinical development program for PF-06410293 consisted of 4 completed clinical studies: 3 single-dose PK studies (B5381001, B5381007, and B5381005) in healthy subjects using a pre-filled syringe (PFS) and a pre-filled pen (PFP) and 1 multidose safety and efficacy study (B5381002) in patients with moderately to severely active RA using a PFS, which included a device substudy using PFP. This program demonstrated the clinical similarity between PF-06410293 and Humira that supported the extrapolation to the Humira indications.

The safety profile of PF-06410293 is consistent with that reported in the US Prescribing Information (USPI) and Summary of Product characteristics (SmPC) of Humira. Data from the PF-06410293 clinical development program did not reveal any new safety risks for PF-06410293. A summary of the clinical safety in the USPI is shown below:

### **Serious Infections**

- Increased risk for developing serious infections.
- Opportunistic infections due to bacterial, mycobacterial, invasive fungal, viral, parasitic, or other opportunistic pathogens have been reported with TNF blockers. Patients have frequently presented with disseminated rather than localized disease.
- Treatment should not be initiated in patients with an active infection, including localized infections.
- Patients greater than 65 years of age, patients with co-morbid conditions and/or patients taking concomitant immunosuppressants, may be at greater risk of infection.

### **Tuberculosis**

- Reactivation of tuberculosis and new onset tuberculosis infections have been reported.
- Treatment of latent tuberculosis infection prior to therapy with TNF blocking agents has been shown to reduce the risk of tuberculosis reactivation during therapy.
- Consider anti-tuberculosis therapy prior to initiation of treatment.

### **Invasive Fungal Infections**

- Consider appropriate empiric antifungal therapy, taking into account both the risk for severe fungal infection and the risks of antifungal therapy.
- Consider consultation with a physician with expertise in the diagnosis and treatment of invasive fungal infections.

### **Hepatitis B Virus Reactivation**

- Use of TNF blockers may increase the risk of reactivation of hepatitis B virus.

### **Malignancies**

- Non-Melanoma Skin Cancer (NMSC): The rate (95% confidence interval) was 0.8 (0.52, 1.09) per 100 patient-years among HUMIRA-treated patients and 0.2 (0.10, 0.59) per 100 patient-years among control-treated patients.
- Lymphoma and Leukemia: The observed rate of lymphomas was approximately 3-fold higher than expected in the general U.S. population according to the Surveillance, Epidemiology, and End Results (SEER) database (adjusted for age, gender, and race). Post-marketing cases of acute and chronic leukemia have been reported in association with TNF-blocker use in RA and other indications. Even in the absence of TNF-blocker therapy, patients with RA may be at a higher risk (approximately 2-fold) than the general population for the development of leukemia.

- *Malignancies in Pediatric Patients and Young Adults:* Malignancies, some fatal, have been reported among children, adolescents, and young adults who received treatment with TNF-blockers (initiation of therapy  $\leq 18$  years of age). These cases were reported post-marketing and are derived from a variety of sources including registries and spontaneous postmarketing reports.

### **Hypersensitivity Reactions**

- Anaphylaxis and angioneurotic edema have been reported following HUMIRA administration.
- Allergic reactions (eg, allergic rash, anaphylactoid reaction, fixed drug reaction, non-specified drug reaction, urticaria) have been observed.

### **Neurologic Reactions**

- Rare cases of new onset or exacerbation of clinical symptoms and/or radiographic evidence of central nervous system, and peripheral demyelinating disease.

### **Hematological Reactions**

- Rare reports of pancytopenia including aplastic anemia, medically significant cytopenia.

### **Heart Failure**

- Worsening congestive heart failure (CHF) and new onset CHF.

### **Autoimmunity**

- HUMIRA treatment may result in the formation of autoantibodies.
- Development of a lupus-like syndrome.

## **2.3. Benefit/Risk Assessment**

PF-06410293 has been approved by the US FDA as a biosimilar to Humira. The clinical benefit of adalimumab (Humira®) is well established and applies to both drugs used in this trial: PF-06410293 and Humira.

The safety profile of adalimumab is well established. The most common adverse reaction to adalimumab are injection site reactions, while the important identified risks include serious infections, malignancies, hypersensitivity reactions, hematologic disorders, gastrointestinal disorders, heart failure and demyelinating disorders.

PF-06410293 is approved by US FDA with the same safety profile as described in the adalimumab (Humira®) USPI and SmPC. Appropriate risk evaluation and mitigation strategies have been incorporated into this protocol.

More detailed information about the known and expected benefits and risks and reasonably expected adverse events (AEs) of adalimumab may be found in the Humira label, which is the SRSD for this study.

### 3. OBJECTIVES, ESTIMANDS, AND ENDPOINTS

Objectives	Estimands	Endpoints
Primary:	Primary:	Primary:

 
To evaluate interchangeability of PF-06510293 and Humira by examining adalimumab steady-state pharmacokinetics in a switching arm (following 3 switches between Humira and PF-06410293) as compared to a non-switching arm (receiving only Humira).
 
	
 
Evaluate the equivalence of primary endpoints (maximum observed concentration (<math>C_{max}</math>) and area under the concentration-time curve over the dosing interval (<math>AUC_{\tau}</math>) obtained during the intensive PK sampling interval) between the switching arm and non-switching arm in participants who meet the PK population criteria, that include criteria for the number and timing of missing doses, availability of PK data, adherence to background therapy, and major protocol deviations related to PK assessment.
 
	
 
<math>C_{max}</math> and <math>AUC_{\tau}</math> obtained during the intensive PK sampling interval.
 

Objectives	Estimands	Endpoints
Secondary:	Secondary:	Secondary:

 
To evaluate other serum adalimumab PK parameters in the switching arm and the non-switching arm.
 
To evaluate the overall safety and tolerability of the switching arm and the non-switching arm.
 
To evaluate immunogenicity of the switching arm and the non-switching arm.
 
	
 
Summarize other serum adalimumab PK parameters, including time at which <math>C_{max}</math> occurs (<math>T_{max}</math>), average concentration over the dosing interval (<math>C_{av}</math>), and apparent clearance (CL/F) obtained during the intensive PK sampling interval in participants who meet the PK population criteria, and predose concentration during multiple dosing (<math>C_{trough}</math>) obtained at scheduled PK sample timepoints in participants who meet the safety population criteria, for the switching arm and non-switching arm.
 
	
 
Other serum adalimumab PK parameters, including <math>T_{max}</math>, <math>C_{av}</math>, and CL/F obtained during the intensive PK sampling interval and <math>C_{trough}</math> obtained at scheduled PK sample timepoints.
 
Safety measures characterized by type, incidence, severity, timing, seriousness and relatedness of treatment-emergent adverse events (AEs) and laboratory test abnormalities.
 
Percent of participants with ADA/NAb and ADA/NAb titers over time.
 

	

• Summarize safety endpoints for the switching arm and non-switching arm in participants who meet the safety population criteria.

• Summarize percent of participants with antidrug antibodies (ADA), and neutralizing antibodies (NAb) and ADA/NAb titers over time for the switching arm and non-switching arm in participants who meet the Safety population criteria.

	
--	---	--

## 4. STUDY DESIGN

### 4.1. Overall Design

This is an open-label, multi-national, 2-arm, randomized, parallel-group study designed to evaluate the interchangeability of the switching arm (PF-06410293 and Humira), compared to non-switching arm (Humira), in participants with moderately to severely active RA on background methotrexate (MTX). For purposes of this protocol, the treatment arm that includes switches between PF-06410293 and Humira will be referred to as the “switching” arm, while the treatment arm that comprises continuous Humira treatment will be referred to as the “non-switching” arm.

This study will enroll a maximum of approximately 420 participants such that approximately 314 evaluable participants complete the study.

Study treatment will be provided through 4 treatment periods. For the first 10 weeks, all participants will receive Humira [Treatment Period (TP) 1]. Upon completion of TP1, participants will be randomized (1:1 ratio) into either the switching or the non-switching arm prior to dosing on Week 10. Randomization will be stratified by 3 body weight groups (Week 10 weight) ( $\geq 40$  kg to  $< 70$  kg;  $\geq 70$  kg to  $< 100$  kg;  $\geq 100$  kg to  $\leq 130$  kg). Participants randomized to the non-switching arm will continue on Humira for the remainder of the study, and participants randomized to the switching arm will continue switching in each TP (TP2: PF-06410293; TP3: Humira; TP4: PF-06410293).

- TP1 (Lead In Period) will begin with the first dose of investigational product on Week 0 (Day 1) and conclude with the completion of Week 10 pre-dose assessments.
- TP2 will begin with the 1:1 randomization of the participants to either the switching arm or the non-switching arm at Week 10. Investigational product dosing for Week 10 will begin after the randomization process in the respective treatment arms and will conclude with the completion of Week 16 pre-dose assessments.

- TP3 will begin with investigational product dosing on Week 16, and conclude with the completion of Week 22 pre-dose assessments.
- TP4 will begin with investigational product dosing on Week 22 and continue through Week 30, where onsite investigational product dosing is scheduled at Weeks 22, 24, 26, 28, and 30, followed by a 2-week PK sampling period from Week 30 to Week 32. TP4 will conclude with end of treatment (EoT) assessments and final dose administration at Week 32.
  - The 2-week PK sampling period starts with Week 30 predose PK collection and ends with predose PK collection on Week 32.
- Safety Follow-Up Period begins after the last investigational product dosing on Week 32, and concludes at completion of the Week 36 assessments. All participants (including early discontinuations) will be followed for at least 28 calendar days from the date of their last dosed investigational product. Week 36 safety follow up may be conducted via phone.

#### 4.2. Scientific Rationale for Study Design

This study design is consistent with recommendations outlined in the FDA Interchangeability guidance and FDA Clinical Pharmacology guidance 2016. These recommendations include lead-in period, switching and non-switching treatment arms, for which the switching arm should have at least 3 switches between the biosimilar and reference products. Furthermore, the duration of each treatment period should be sufficient to establish PK steady state, with PK samples collected at the end of the last treatment period in both treatment arms for determination of steady state PK parameters. PK parameters should be analyzed using a standard bioequivalence (BE) approach with acceptance margins of 80.00% to 125.00%.

Specific details regarding statistical approaches to data analysis for this study are discussed further in [Section 9](#).

This study is also designed to evaluate safety and immunogenicity after several investigational product switches between the switching and non-switching arms.

#### 4.3. Justification for Dose

The 40 mg dose is the recommended dose for RA participants in the HUMIRA and PF-06410293 labels for moderately to severely active RA patients. Dose modification is not allowed in this trial to avoid potential confounding factors that could impact ADA formation and PK, as well as safety (see [Section 6.6](#)).

#### 4.4. End of Study Definition

A participant is considered to have completed the study if he/she has completed all treatment periods of the study, including the EoT visit (Week 32). The final safety follow-up is at Week 36, which may be done by phone. Early discontinuation from investigational product requires participants to return as soon as possible after the last dose of investigational product

for an EoT visit. A safety follow-up (may be done by phone) at least 28 calendar days after the last investigational product is also required.

The end of the study is defined when the last participant in the trial completes the date of last scheduled visit or contact as shown in the [SoA](#).

## 5. STUDY POPULATION

This study can fulfill its objectives only if appropriate participants are enrolled. The following eligibility criteria are designed to select participants for whom participation in the study is considered appropriate. All relevant medical and nonmedical conditions should be taken into consideration when deciding whether a particular participant is suitable for this protocol.

Prospective approval of protocol deviations to recruitment and enrollment criteria, also known as protocol waivers or exemptions, is not permitted.

### 5.1. Inclusion Criteria

Participants are eligible to be included in the study only if all of the following criteria apply:

#### Age and Sex:

1. Male or female participants between the ages of 18 (or the minimum country-specific age of consent if >18) and 70 years, inclusive, at Visit 1 (Screen 1).
  - Refer to [Appendix 4](#) for reproductive criteria for male ([Section 10.4.1](#)) and female ([Section 10.4.2](#)) participants.

#### Type of Participant and Disease Characteristics:

2. Participants who are willing and able to comply with all scheduled visits, treatment plan, laboratory tests, lifestyle considerations, and other study procedures.
3. Diagnosis of rheumatoid arthritis (RA) based on 2010 American College of Rheumatology (ACR)/European League Against Rheumatism (EULAR) classification criteria for RA for at least a 4 month duration.
4. Moderately to severely active RA disease based on local standard of care.
5. Must have received oral, subcutaneous (SC), or IM methotrexate for at least 12 weeks and been on a stable dose for at least 4 weeks prior to first dose of investigational product on Day 1 of TP1. The stable dose must be 10 to 25 mg per week, with the exception of 6 to 25 mg per week where 6 mg per week is a recommended initial dose by local guidance or standard of care.

6. Stable dose of oral folic acid (at least 1 mg/day on  $\geq 5$  days per week) or oral folinic acid ( $\geq 5$  mg once per week) supplementation for at least 21 days prior to the first dose of investigational product on Day 1 of TP1. In countries which do not have approved folic acid 1 mg or folinic acid 5 mg presentations, a regimen of folic acid of  $\geq 5$  mg weekly is acceptable.

**Weight:**

7. Body mass index (BMI) of 18 to 45 kg/m^2 and a total body weight of  $\geq 40$  kg (88 pounds) to  $\leq 130$  kg (287 pounds).

**Informed Consent:**

8. Capable of giving signed informed consent as described in [Appendix 1](#), which includes compliance with the requirements and restrictions listed in the informed consent document (ICD) and in this protocol.

**5.2. Exclusion Criteria**

Participants are excluded from the study if any of the following criteria apply:

**Medical Conditions:**

1. Evidence or history of nervous system demyelinating diseases (including multiple sclerosis, optic neuritis, Guillain-Barré syndrome).
2. History of seizure disorder requiring treatment in the previous 5 years prior to Screening.
3. History of or active significant infection defined by:
  - a. History of recurrent (more than one episode) limited herpes simplex which requires current chronic antiviral therapy, or disseminated (a single episode) herpes simplex.
  - b. History of disseminated or recurrent infection with Epstein Barr virus (EBV), human papilloma virus (HPV), or varicella zoster. A single, limited episode in the past is not exclusionary.
  - c. Any infection requiring hospitalization or parenteral antimicrobial therapy judged clinically significant by the investigator within 6 months prior to first dose of investigational product.
  - d. History of an infected joint prosthesis at any time, with the prosthesis still in situ.
  - e. SARS-CoV2 infection (COVID-19) should be considered clinically significant, local guidelines on COVID-19 and medical judgement should be followed.

- f. Any other active infection considered to be clinically significant as assessed by the investigator.
4. Known or screen test confirmed positive for human immunodeficiency virus (HIV), hepatitis B virus, or hepatitis C (HCV) virus (please see [Section 8.2.8](#) for details on testing).
  - a. Positive for HIV.
  - b. Positive hepatitis B surface antigen (HBsAg).
  - c. Positive hepatitis B core antibody (HBcAb) without positive hepatitis B surface antibody (HBsAb) (unless it is documented that hepatitis B DNA test is negative).
  - d. Positive hepatitis C antibody (HCV Ab) results and positive confirmatory HCV ribonucleic acid (HCV RNA) results.
5. Evidence of current or recent history of uncontrolled, clinically significant hematological, renal, endocrine, pulmonary, gastrointestinal, hepatic, infectious, psychiatric, neurologic, allergic, or cardiovascular disease including evidence or history of moderate or severe heart failure (NYHA Class III/IV) or Screening 12-lead electrocardiogram (ECG) that demonstrates clinically relevant abnormalities which may affect participant safety, and participants who are contraindicated for treatment with adalimumab in accordance with the approved local label.
6. History of any lymphoproliferative disorder (eg, EBV related lymphoproliferative disorder, lymphoma, or leukemia). Evidence or history of a malignancy within the past 5 years (with the exception of adequately treated or excised non-metastatic basal cell or squamous cell cancer of the skin, or cervical carcinoma in situ with no evidence of recurrence).
7. History of recurrent inflammatory joint disease other than RA (eg, post infectious arthritis, gout, etc.) or history of any other autoimmune rheumatic diseases (eg, vasculopathies, spondyloarthropathies, etc.) other than Sjogren's syndrome.
8. Significant trauma or surgical procedure within 4 weeks prior to first dose of investigational product.
9. History of severe allergic or hypersensitivity or anaphylactic reaction to a biologic drug or to active or inactive components of the investigational product.
10. Other acute or chronic medical or psychiatric condition including recent (within the past year) or active suicidal ideation or behavior or laboratory abnormality that may increase the risk associated with study participation or investigational product administration or may interfere with the interpretation of study results and, in the judgment of the investigator, would make the participant inappropriate for entry into this study.

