		Added clarification in Section 1.1 that immune-related safety will be described for the safety population including injection site reactions, hypersensitivity, anaphylaxis and angioedema.
		CCI [REDACTED]
		Added utilization of home healthcare service as an option during the 2 week PK

Document History		
Document	Version Date	Summary of Changes and Rationale
		sampling period in SoA, Table 1 and Section 8.5.
		Clarified that only applicable adalimumab injection details will be recorded in the electronic Participant Dosing Log in SoA, Sections 6.1.1 and 6.4.
		
Clarifications made to the following inclusion/exclusion criteria to stay consistent with Humira label:
 
 
• Removal of Inclusion Criterion 7 as it is a duplication of Exclusion Criterion 14. Additionally, clarification is made to Exclusion Criterion 14.
 
• Clarification provided to Section 5.2, Exclusion Criteria 4c and Section 8.2.8 that confirmed positive HIV, Hepatitis B and Hepatitis C are excluded. More specifically, Hepatitis B DNA test has been added.
 
• Clarification provided on prohibited biologic therapy in Exclusion Criterion 13, Section 6.5 and Appendix 9 (Prohibited Concomitant Medication and Procedures).
 
• Added new Exclusion Criterion 18 that unstable dose of oral and intramuscular (IM) corticosteroid is prohibited. Updated Sections 6.5.2 and removed Appendix 9 (Oral Corticosteroid in FAP).
 

		Add clarification to Exclusion Criterion (#3) that active significant infection,

Document History		
Document	Version Date	Summary of Changes and Rationale
		eg, SARS-CoV2 (COVID-19) infection and any active infection considered to be clinically significant by the investigator should be excluded. Updates are also made in Sections 7.1.1 and 7.1.2.
		Language in Section 7.2 has been updated to follow Pfizer’s latest protocol template.
		Updated population for analysis in Section 9.3 and AE analysis in Section 9.4.2.1.
		Updated contraceptive requirements to follow Humira label for male participants Section 10.4.1. Additionally, removed text “highly” from highly effective contraceptive methods in Exclusion Criterion 24, Sections 5.3.1 and 10.4.4 to keep consistent with Humira label.
		Additional typographic errors were corrected and editorial changes provided, as deemed necessary, throughout the protocol.
		Blood sample volume was updated in Section 8.5

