## **6.5.1. Stable Background Therapies**

### **6.5.1.1. Methotrexate**

Adalimumab must be administered concomitantly with a stable dose of MTX throughout the course of study treatment.

The administration of MTX, including dosage, laboratory testing, follow-up care (including contraception requirements), and contraindications should be performed according to local standards of care throughout the study.

At study entry, participants must have received oral or IM MTX for at least 12 weeks and have been on a stable dose of 10 to 25 mg per week for at least 4 weeks prior to first dose of investigational product. In geographic regions where 6 mg per week is a recommended initial dose by local guidance or standard of care, a stable dose of as low as 6 mg per week for at least 4 weeks prior to first dose of investigational product will be permitted.

Participants are required to continue their stable dose of MTX background therapy throughout the study. Dose reduction of MTX therapy during the study treatment is not recommended, with the exception of significant intolerance, and the dose reduction must be documented with the investigator's medical justification. Participants will not be discontinued from study treatment following a justified dose reduction of MTX, unless the MTX is adjusted below the minimal required dosage level of 7.5 mg/week (or a dose as low as 6 mg/week in geographic regions where permitted by local guidance or standard of care).

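### The protocol's own label summary advises against starting adalimumab during any active infection, including a localized one, but no text tells the site to postpone the first dose for an infection judged minor

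*Protocol*

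**What the plan says.** Protocol Section 2.2.1 introduces its list of risks with "A summary of the clinical safety in the USPI is shown below". Under Serious Infections, the first risk listed, it states: "Treatment should not be initiated in patients with an active infection, including localized infections". The same list adds that "patients taking concomitant immunosuppressants, may be at greater risk of infection". Section 2.3 says that fuller risk information "may be found in the Humira label, which is the SRSD for this study", which makes the label the single reference safety document.

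Entry is governed by Section 5. The stem of exclusion 3 is limited to significant infection. Items 3a to 3e cover named infections or defined categories. Item 3f takes in the rest: "Any other active infection considered to be clinically significant as assessed by the investigator". The amendment summary shows that this filter was put in on purpose, recording that "any active infection considered to be clinically significant by the investigator should be excluded".

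Section 6.5.1.1 requires methotrexate for everyone: "Adalimumab must be administered concomitantly with a stable dose of MTX throughout the course of study treatment".

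**The concern.** The label summary sets no severity threshold for starting treatment, while 3f does, and leaves it to the investigator's judgment. A site that regards a localized infection as not clinically significant can apply 3f exactly and give the first TNF-blocker injection in a situation that Section 2.2.1 says to avoid.

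What is at stake is participant safety at initiation. The higher-risk groups named in the label summary fit this trial closely. Every participant takes methotrexate, leflunomide and corticosteroids are also permitted (Sections 6.5 and 6.5.2), and the age limit of 70 admits some patients over 65, another group that the summary names. Section 2.3 says that suitable risk mitigation has been built into the protocol, so one would expect this precaution to have an operational counterpart. Deciding whom to exclude and deciding when to give the first dose are separate questions, and the protocol answers only the first.

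**Working it through.** No plan figure is in dispute, so the check compares texts: does any current provision tell a site to postpone dose 1 for an active infection judged minor?

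1. **Section 2.2.1.** Advises against initiation with any active infection, localized ones included. It is background, not an entry rule.
2. **Exclusions 3a to 3e, 4 and 20.** These cover particular herpes, EBV, HPV and zoster histories, infection needing hospital or parenteral treatment, an infected prosthesis, COVID-19, HIV, hepatitis B and C, and tuberculosis. A minor localized infection outside these groups is not reached.
3. **Exclusion 3f.** Reaches other active infections only above the clinical-significance threshold.
4. **Exclusion 5, final clause.** Excludes "participants who are contraindicated for treatment with adalimumab in accordance with the approved local label". The documents do not say whether any local label lists a localized infection as a contraindication, so cover here can be neither confirmed nor ruled out.
5. **Exclusion 10 and the opening of Section 5.** Exclusion 10 covers an acute condition that may raise the risk of dosing, if the investigator judges entry inappropriate. Section 5 opens by asking that all relevant conditions be weighed. Both permit a hold. Neither instructs one.
6. **Day 1 check (Schedule of Activities; Section 6.3.1).** The same criteria are checked again at Week 0, and dispensing depends on eligibility. There is no separate infection check or hold.
7. **Section 7.1.1.** Permits an interruption for an infectious adverse event during Treatment Periods 1 to 3 and the first two doses of Period 4. Section 4.1 starts Period 1 with the first dose, so this rule concerns treatment under way and does not govern its start.

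The result is that holding the participant is allowed under items 4 and 5, but no provision requires it. There is express guidance on infection once dosing has begun, and none at initiation, which is the moment the label summary addresses.

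The primary analysis is untouched. The first dose comes ten weeks before randomization. Because Period 1 begins with that dose, a deferral moves Day 1 and does not create a missed dose under the PK population rules.

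**The case against.** The strongest reply is that the governing text already works. An investigator facing an active infection before a TNF blocker may call it clinically significant under 3f, use exclusion 10, check the local label under exclusion 5, or rely on the general instruction that opens Section 5. Criteria are checked at Screening and on Day 1, and Section 5.4 has retest and rescreen routes. Harm requires the investigator to see no concern under any of these. The 3f filter was also a deliberate choice, and a rule of deferral until resolution without exception would override it: a trivial or chronic infection that never fully clears would become an exclusion.

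Much of this stands. It makes the gap smaller, and it is why the deferral rule needs an exception for controlled chronic or slow-to-clear infections. It does not remove the gap, because discretion to hold is not an instruction to hold, and practice may differ between sites in a multinational trial.

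A reader might go further and infer that 3f breaches a binding label requirement or is a drafting error. The documents do not support that: Section 2.2.1 is background, and Amendment 1 added the 3f wording on purpose. Nor do they support the inference that many infected participants would be dosed, since they give no frequency.

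**Conclusion.** The point holds as a modest participant-safety alignment. The plan states a precaution about starting treatment, drawn from the label it uses as its reference safety document, and gives sites no matching instruction for the first dose. The gap is confined to participants with an active infection on Day 1 that is outside the named categories, is judged not clinically significant, and is not held under exclusions 5 or 10 or the opening of Section 5. The number of such participants cannot be derived from the documents.

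The conclusion assumes that Section 2.2.1 reports the label faithfully, which cannot be checked here, and that local labels do not already make every localized infection a contraindication. If they do, exclusion 5 closes the gap and the added text is only a reminder. It would be wrong to read this as a flaw in the design's validity: sample size, randomization and the pharmacokinetic comparison are unaffected.

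**What to change.** Keep 3f as the exclusion rule and add directly beneath it:

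> If any other active infection, including a localized infection, is present on Day 1, the first dose is deferred until the infection has resolved or, for a chronic or slow-to-clear minor infection, is documented by the investigator as controlled. If the deferral exceeds the 6-week screening period, the participant may be rescreened under Section 5.4.

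The second half of the first sentence keeps a role for investigator judgment, so that deferral does not become exclusion by default.

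The change is two sentences in an amendment. Each deferred participant needs an extra visit. Some will need time-limited screening tests repeated, or full rescreening. The first dose would be held to a stricter rule than later doses, for which Section 7.1.1 only permits a hold.

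On repeat testing, QuantiFERON must fall within 6 weeks (42 days) before dose 1 for those not exempt under Section 8.2.6. A test drawn d days before the planned Day 1 therefore stays valid for 42 − d more days: 41 if d = 1, and 0 if d = 42. The documents do not give a typical d. This is test validity only, not the time available for deferral, because the screening period may run out first. If screening opened on Day −42 and the test was drawn on Day −1, the test has 41 days left but the screening period has essentially none.
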